# Background

Chronic venous disease (CVD) has various clinical presentations and the most commonly known symptom is varicose veins. Other symptoms include pain, oedema, and cutaneous changes of the lower legs such as hyperpigmentation, eczema, atrophie blanche (white scar tissue) and lipodermatosclerosis (induration caused by the fibrotic process of the subcutaneous fat). Chronic venous disease can be classified with the clinical, aetiologic, anatomical, and pathophysiological classification (CEAP-classification) in which the clinical signs are graded into six classes; C0-C6 (Table 1). CVD includes all symptoms and signs, whereas chronic venous insufficiency (CVI) refers to a more advanced stage of CVD (i.e. C4-C6) (12).

C0	No visible or palpable signs of venous disease
C1	Telangiectasies or reticular veins
C2	Varicose veins
C3	Oedema without skin changes
C4a`	Pigmentation or eczema
C4b	Lipodermatosclerosis or atrophie blanche
C5	Healed venous ulcer
C6	Active venous ulcer

# **CEAP Clinical classification of chronic venous disease**

The prevalence of CVD varies among the different stages of the disease. A large worldwide study of the Vein Consult Program showed a prevalence of clinically significant CVD of more than 60% in the general population (4). Varicose veins are the most common manifestation

of CVI with a prevalence up to 30% in adult population (1,2,3). The prevalence of active and healed ulcers is approximately 1% of the adult population (5). Since delayed healing and recurrence are very common, the prognosis of venous ulceration is poor (6).

The high prevalence and the chronic nature of venous disease have a considerable socioeconomic impact. A study conducted in the United States and the United Kingdom showed that venous ulcers cause a decrease of 2 million working days per year (7) and the National Health Service (NHS) spends approximately 1-3% of the total health care budget on the treatment of CVD (8,9).

Graded compression stockings are the primary conservative treatment in patients with CVI. A significant improvement can only be achieved with a good compliance (10). Reduced adherence to compression therapy is a well-known and major issue in the treatment of patients with CVD (13). Patients with clinical CEAP classification C4 venous disease, or higher, have an increased risk of venous ulceration. Non-compliance with compression hosiery and deterioration of the skin condition increases this risk. In literature the non-compliance ranged from 22%-67% (13 - 17). The most common reasons for non-compliance are inapplicability, the perception of inefficacy and the lack of comfort (13). However, the strategy to properly address non-compliance remains unknown.

Standard compression stockings reduce the symptoms of pain and oedema, facilitate the healing of ulcers, and prevent the recurrence of venous ulcers (11), but they do not improve the skin condition. Copper has been shown to promote angiogenesis and therefore it could support wound healing and possibly improve skin condition. Copper has also been shown to have strong antimicrobial properties. It has been shown in observational, non-randomised trials that improvement of the skin condition could be seen within two weeks (33,34). When no change in skin condition is seen within four weeks, it is unlikely to be seen at all.

# Antimicrobial copper

Copper was primarily known for its antimicrobial effect and has been used for hygienic purposes for centuries (18). With the increase in antibiotic resistant bacteria causing nosocomial infections, copper has become a popular subject of recent research. There are many laboratory studies showing the biocidal effect of copper on a wide range of microbes such as bacteria, fungi and viruses (21,22). Copper has also been proven to be effective against Methicillin-resistant Staphylococcus aureus (MRSA) (19) and Vancomycin-resistant Enterococci (VRE) (20). The use of copper surfaces in the hospital has been evaluated in several clinical studies showing significant reductions in bacterial colonisation on copper surfaces compared to standard materials (23). After the use of copper as a biocidal contact surface, the use of copper impregnated textiles was explored. Currently, there is a great variety in products available containing copper impregnated textiles such as socks, pyjamas, underwear, bed linen, face masks, stockings and wound dressings, but there is a paucity of clinical research. There has been a clinical study on the effect of copper impregnated socks in patients suffering from tinea pedis showing a significant improvement or resolution of the infection after wearing these socks for two weeks (24).

## Wound healing

It has also been proven that copper is essential for the process of wound healing. Copper is assumed to be involved in several processes crucial for wound healing (25). A key role in wound healing is angiogenesis. It has been shown that copper induces the production of vascular endothelial growth factor (VEGF) and therefore stimulates angiogenesis (26). Furthermore, copper promotes wound healing due to an elevation in integrin expression (27); enhancement of fibrinogen stabilisation (28) and up-regulation of several enzymes essential for matrix remodelling and cell growth (29). Several laboratory studies have

demonstrated an association between a copper dependant enzyme, lysyl oxidase (LOX), and skin ageing and pathological skin conditions (30).

#### **Safety**

The dermal exposure to copper is considered safe as copper is not only an essential element for normal skin function but also essential for the immune system and blood coagulation (31). In contrast to microorganisms, human skin cells have the ability to metabolise and utilise copper (32) and therefore the development of adverse reactions are unlikely (33,35).

Our hypothesis is that copper impregnated stockings promotes wound healing and improves the skin condition in patients with lipodermatosclerosis secondary to CVI.

# Aim

To investigate the impact of copper impregnated stockings on subjective and objective outcomes in patients with lipodermatosclerosis secondary to venous insufficiency.

# **Objectives**

# Primary:

To assess the effect of copper stockings on symptoms in patients with lipodermatosclerosis secondary to venous insufficiency.

## Secondary:

To assess the effect of copper stockings on skin condition in patients with lipodermatosclerosis secondary to venous insufficiency.

# Methodology

This is a randomised controlled pilot study to assess the feasibility of copper impregnated stockings. All patients with CEAP classification 4 in both legs and venous disease identified by venous duplex will be recruited from the vascular clinics within Croydon Health Services over a period of three months. All patients will be given a patient information sheet describing the study prior to consent (Appendix 1 Patient Information Sheet). Patients will be giving adequate time to read the information. Informed consent and the agreement for photography of their legs will be obtained (Appendix 2 Informed Consent). Patients will be assessed at baseline and at 2, 4 and 8 weeks follow-up.

The inclusion criteria are:

- Male or female patients
- CEAP classification 4 in both legs
- Venous disease identified by venous duplex
- Ability to understand and read the patient information sheet (in English)
- Ability to give informed consent

The exclusion criteria are:

- Inability to give consent
- Pregnancy
- Current ulceration
- Wilson's disease
- Allergy to copper
- Arterial insufficiency of the lower extremities

# Copper impregnated stockings

All patients will be asked to wear compression stockings (14-18mmHg). These closed-toe and below-the-knee stockings are made of 88% nylon, 5% elastin, and 7% spandex and come in various sizes. One of the pair will have copper oxide ions permanently attached to

CIVIL Protocol Version 3 (25/03/2015) 15/LO/0974

the nylon fibres and these stockings will contain 2-3% copper ions. The patients will wear a copper stocking on one leg (study leg) and a non-copper stocking on the other (control leg). Both the patients and the clinicians will be blinded to the copper impregnated stocking.

# **Randomisation**

All stockings are marked with an 'L' for the left or 'R' for the right foot. The manufacturer has randomly marked the copper stockings with an 'L' or 'R' and paired these with a non-copper stocking. A closed envelope will contain the unique numbers of all the pairs of stockings and the information on which sock contains the copper. This envelope will remain closed for the whole recruitment period.

# Patient data, history and physical examination:

Demographic data such as age, ethnicity, height and weight will be collected (Appendix 3 Datasheet). Past medical history such as concomitant (chronic) diseases and the use of medications will be obtained. At each visit, subjective symptoms will be obtained using the Aberdeen Varicose Veins Questionnaire (AVVQ). For obtaining objective signs, the CEAP classification and the Venous Clinical Severity Scoring (VCSS) will be performed for grading the severity of the venous insufficiency per leg individually, and photographs with the Eykona® 3D camera will be taken. All datasets will be coded and anonymised. The data will be stored in a secure room within the Trust. All electronic data will be stored within password protected IT system within the Trust, which is only accessible by the clinical and research team.

#### Aberdeen Varicose Veins Questionnaire

This questionnaire is specific for varicose vein disease but it also addresses important elements of venous insufficiency in general. The AVVQ (appendix 4 Datasheet) is a validated questionnaire and it consists of 13 questions on signs and symptoms such as pain, oedema, itching, purple discoloration, eczema and skin ulceration. It also addresses social

CIVIL Protocol Version 3 (25/03/2015) 15/LO/0974

issues such as compression stocking usage and the effect of the disease on daily life. The AVVQ is the only validated questionnaire on vascular disease where most questions address each leg separately and therefore provides the ability to compare the two legs. The scoring of the questionnaire is from 0, which indicates no effect on the patient, to 100, which indicates a severe effect.

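### The AVVQ is chosen to compare the two legs, but the plan defines no leg-level AVVQ score, and a change from baseline in a patient total cannot isolate a copper effect

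*Combined protocol and SAP*

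**What the plan says.** All references are to the combined protocol and SAP.

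- **Objectives, Primary:** "To assess the effect of copper stockings on symptoms in patients with lipodermatosclerosis secondary to venous insufficiency".
- **Copper impregnated stockings:** every patient has one copper leg and one control leg, and both stockings are compression stockings.
- **Patient data, history and physical examination:** the AVVQ is the tool for subjective symptoms at each visit. CEAP and VCSS are listed under objective signs, and the per-leg wording belongs to them: they "will be performed for grading the severity of the venous insufficiency per leg individually". Nothing equivalent is said of the AVVQ.
- **Aberdeen Varicose Veins Questionnaire:** the instrument has 13 questions and is preferred as the only validated one "where most questions address each leg separately and therefore provides the ability to compare the two legs". It also covers social "issues such as compression stocking usage and the effect of the disease on daily life". The scoring is then given in one sentence: "The scoring of the questionnaire is from 0, which indicates no effect on the patient, to 100, which indicates a severe effect".
- **Statistical analysis:** CEAP, VCSS and AVVQ at weeks 2, 4 and 8 are set against baseline. A copper-versus-control comparison is stated only for the dimensions and area of the skin changes. A mixed model is planned for change over time, with no leg or treatment term named.

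**The concern.** The reason given for choosing the AVVQ is a property of its leg-specific questions. The scoring given for it is a property of the patient. Nothing in the supplied text connects the two: there is no list of leg-specific questions, no leg score with a range, and no rule for questions that are not asked per leg.

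This goes beyond an omitted contrast. A single total takes the same value for the copper leg and the control leg, so adding a copper-versus-control comparison to the Statistical analysis section would not help unless a leg-level score were defined as well.

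The primary objective is at stake. Both legs wear compression during the study, so a fall in a patient total may reflect compression, time or copper, and could be reported as a copper effect without grounds. The pilot is also meant to supply figures for the power calculation of a larger study. The variability of a patient total does not give the variability of a within-patient leg difference.

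**Working it through.** **The plan's own figure.** The only design figure is a sample size of 15, based on three-month prevalence at the hospital. No significance level, power, effect size or standard deviation is given, so there is no calculation to reproduce. The point does not depend on one.

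**Check 1: can a copper effect be estimated?**

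Inputs from the protocol: 15 patients; baseline and weeks 2, 4 and 8; one copper leg and one control leg per patient.

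Model parameters: 15 patient intercepts + 3 visit effects + 3 copper-by-visit effects = 21.

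- *One total per patient.* Rows: 15 × 4 = 60. Every patient has exactly one copper leg, so the copper term takes the same value in every row (coded 0.5 here). Each copper-by-visit column is then 0.5 times the matching visit column. The three copper columns add nothing, and the rank is 15 + 3 = 18 of 21. None of the three copper effects can be separated from time.
- *One score per leg.* Rows: 15 × 2 × 4 = 120. The copper term is 1 on the study leg and 0 on the control leg. The rank is 21 of 21, and all three copper effects can be estimated.

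This result needs no assumed effect size, standard deviation or item weight. It is conditional on there being one AVVQ value per patient per visit.

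**Check 2: what would a change in the total mean?**

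Assumptions, not in the documents: leg-specific questions carry a share *w* of the total weight, split equally between legs, with *w* from 60% to 100%; the remaining questions do not change. With copper-leg change *c* and control-leg change *k*:

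change in total = *w* × (*c* + *k*) / 2; leg difference = *c* − *k*

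| *c* | *k* | Change in total, *w* = 60% | Change in total, *w* = 100% | Leg difference |
|---|---|---|---|---|
| −10 | 0 | 0.6 × (−10)/2 = −3.0 | −5.0 | −10 |
| −5 | −5 | 0.6 × (−10)/2 = −3.0 | −5.0 | 0 |
| 0 | −10 | 0.6 × (−10)/2 = −3.0 | −5.0 | +10 |

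At any one value of *w*, benefit from copper, no copper effect and harm from copper all give the same change in the total. The value of *w* alters the size of that change but not the ambiguity.

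**The case against.** Four objections carry weight.

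1. **Pooling is not stated.** A reader might infer that the protocol sums the two legs into one number. No sentence says so. The 0 to 100 sentence can be read as a description of the instrument's range, and the sentence before it declares an intention to compare legs. The Appendix 4 datasheet, which may hold a scoring sheet, is not in the supplied text. This stands: the supportable statement is that no leg-level score is defined in the text available.
2. **The wording of the analysis section proves little.** It omits the leg for CEAP and VCSS too, which are graded per leg elsewhere. This also stands: the phrase does not show that the AVVQ is patient-level. It still leaves the AVVQ with only a baseline comparison.
3. **There is leg-level symptom information.** A reader might infer that the primary objective has no leg-level symptom measure at all. That goes too far: the VCSS includes pain and oedema and is graded per leg. However, the protocol places the VCSS under objective signs and assigns subjective symptoms to the AVVQ. What is missing is a leg-level patient-reported score.
4. **The rank check assumes its premise.** It starts from one value per patient, so it shows the consequence of such a score and not that the sponsor will use one. That is correct, and the conclusion is worded accordingly.

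It can also be said that this is a 15-patient pilot and that the leg-specific answers will be collected anyway, so no data are lost. That makes the repair cheap. It does not make it unnecessary, because the scoring rule should be fixed before allocation is known.

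**Conclusion.** The point holds in this form: the protocol justifies the AVVQ by its capacity to compare legs, describes only a patient-anchored 0 to 100 scale, plans only a comparison with baseline, and defines no leg-level AVVQ score in the supplied text. Followed as written with one total per patient, the plan makes none of the three copper-by-visit effects on the AVVQ estimable. Under the assumed weights, a fall of 3 to 5 points in the total is compatible with leg differences from −10 to +10.

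The main assumption is that no leg score is defined in the datasheet that was not supplied. If one is, it should be brought into the protocol text and the point reduces to stating the leg comparison.

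Two further inferences are not supported. A reader might want to work out what fraction of the total the copper leg contributes, and hence how far a copper effect is diluted; the documents give neither item weights nor the number of leg-specific questions. A reader might also take stocking use to be a question shared by both legs; the protocol calls it a social issue but does not say whether it is asked per leg.

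This should be corrected, because it bears on the primary objective, but it requires no change to the design or to data collection.

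**What to change.** Before the allocation envelope is opened, amend the Aberdeen Varicose Veins Questionnaire and Statistical analysis sections as follows.

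- Define a right-leg and a left-leg AVVQ score for each patient at each visit, built only from questions asked separately for each leg.
- After checking the questionnaire itself, name those questions, their weights and the resulting range.
- Leave questions not asked per leg out of the leg scores. Settle from the questionnaire which ones these are.
- State the copper-leg versus control-leg comparison of these scores as the symptom analysis for the primary objective. Fit it in the mixed model with legs nested within patient and copper-by-visit terms.
- Keep the 0 to 100 total as a description of overall patient burden only, not as evidence about copper.
- Report the variability of the within-patient leg difference, since the later power calculation needs it.

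The cost is a scoring rule and some SPSS syntax, with no extra visits, patients or questions. The real downside is that a leg subscore does not inherit the validation of the full questionnaire, and this should be stated as a limitation.

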#### CEAP

Chronic venous disease can be classified with the clinical, aetiologic, anatomical, and pathophysiological (CEAP) classification (appendix 4 Datasheet). The clinical element is scored from 0 to 6 with increasing disease severity. The aetiological element indicates if the venous disease has a congenital, primary or secondary origin. The anatomical element denotes if the veins involved are superficial, deep or perforating. The pathophysiological element indicates the presence of reflux or obstruction.

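### The objectives are for lipodermatosclerosis (C4b), but entry admits any class 4 legs, so the results would describe a broader population; the CEAP score as worded may also miss a move from C4b to C4a

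*Combined protocol and SAP*

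**What the plan says.** - **CEAP table (Background).** Class 4 is split. C4a is "Pigmentation or eczema" and C4b is "Lipodermatosclerosis or atrophie blanche". The class below, C3, is "Oedema without skin changes".
- **Target population.** The hypothesis, at the end of the Safety section, is that copper stockings promote wound healing and that their use "improves the skin condition in patients with lipodermatosclerosis secondary to CVI". The primary objective is "To assess the effect of copper stockings on symptoms in patients with lipodermatosclerosis secondary to venous insufficiency" and the secondary objective is "To assess the effect of copper stockings on skin condition in patients with lipodermatosclerosis secondary to venous insufficiency". The Aim names the same patients.
- **Entry (Methodology).** The severity criterion is "CEAP classification 4 in both legs". The other inclusion criteria cover sex, duplex-identified venous disease, reading ability and consent. No inclusion or exclusion criterion mentions lipodermatosclerosis, C4b or induration.
- **CEAP as an outcome.** The CEAP section states: "The clinical element is scored from 0 to 6 with increasing disease severity". The Statistical analysis section compares CEAP, with the VCSS and the AVVQ, at 2, 4 and 8 weeks against the baseline scores.
- **Use of the data (Sample size calculation).** There are 15 patients, a number set by local prevalence over three months. The pilot data are to support a power calculation for a multicentre study.

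**The concern.** The objectives name one subclass of class 4, while entry uses the whole class. If the plan is followed exactly, some of the 15 patients may have no lipodermatosclerosis in either leg, yet they contribute to every copper-versus-control comparison. A conclusion about lipodermatosclerosis would then rest partly on patients who do not have it, and the effect and SD carried into the next trial's power calculation would belong to a different population.

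The same loss of the letter may affect CEAP as an outcome. Every leg enters at class 4. On a plain 0 to 6 score, a leg whose lipodermatosclerosis clears while pigmentation remains does not move. A CEAP result of no change could then be read as evidence against a skin benefit that the score could not have shown.

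**Working it through.** The plan gives no alpha, power, effect size or SD, so there is no calculation of its own to reproduce. The check sets the sections side by side and then sizes the consequences under stated assumptions.

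**1. Entry against objectives.** A patient with pigmentation or eczema alone in both legs is C4a in both legs. That is class 4 in both legs, so the patient is eligible. The objectives require lipodermatosclerosis, which the table lists under C4b only. The mismatch follows from the text and needs no assumption.

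**2. The 0 to 6 score, if the letter is not kept.** C4a = 4 and C4b = 4, so a move from C4b to C4a is 4 − 4 = 0. The score falls only at C3 or lower, when all class 4 skin change has gone. With ordered steps C3, C4a, C4b, C5, C6, the same move is −1 step.

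If k of 15 copper legs made this move and no control leg did, the 0 to 6 means would be 4.00 and 4.00 for every k. With the letter kept, the exact McNemar p-value for k against 0 discordant pairs is 2 × 0.5^k: 0.031 for k = 6 and 0.002 for k = 10. These k are illustrations, not forecasts.

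**3. Effect of a mixed group on the pilot estimates.** The inputs are all assumptions, because the documents give none of them:
- C4a share q = 0.2, 0.4 or 0.6
- standardised paired effect d = 0.5 in patients with lipodermatosclerosis
- paired t-test, two-sided 5%, 80% power

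Patients with lipodermatosclerosis alone would need n = 34. For the mixed group:
- *Half the effect in C4a patients, same SD:* d_mix = (1 − q/2)d / √(1 + q(1 − q)(d/2)²)
- *No effect in C4a patients, zero SD:* d_mix = (1 − q)d / √((1 − q) + q(1 − q)d²)
- *No effect in C4a patients, same SD:* d_mix = (1 − q)d / √(1 + q(1 − q)d²)

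| q | Non-C4a patients of 15, 15(1 − q) | Half effect: d_mix, n | No effect, zero SD: d_mix, n | No effect, same SD: d_mix, n |
|---|---|---|---|---|
| 0.2 | 12 | 0.448, 42 | 0.436, 44 | 0.392, 53 |
| 0.4 | 9 | 0.397, 52 | 0.369, 60 | 0.291, 95 |
| 0.6 | 6 | 0.347, 67 | 0.295, 93 | 0.194, 210 |

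If C4a patients respond equally, n stays at 34 for every q. The counts 12, 9 and 6 are upper limits for lipodermatosclerosis in both legs. C4b also covers atrophie blanche alone, and some patients may have one C4a leg and one C4b leg.

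**4. Precision in the subgroup.** The 95% limits for an SD, as multiples of its estimate, are √(df/χ²) at the 97.5% and 2.5% points: 0.73 to 1.58 for n = 15, 0.68 to 1.92 for n = 9, and 0.62 to 2.45 for n = 6.

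**The case against.** **The plan may keep the letter.** The Background introduces the scale as C0 to C6 and then prints C4a and C4b as separate rows, so the 0 to 6 range may be shorthand for a scale that contains the split. The Appendix 4 datasheet, which was not available for this review, may record it. This stands. A reader might infer that CEAP certainly scores the improvement as no change. The documents do not establish that; they only fail to say that the letter is used.

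**Other measures cover the skin.** The VCSS scores pigmentation, inflammation and induration, and the Eykona system measures areas of induration, erythema, hyperpigmentation and white atrophy. CEAP is not named as the primary endpoint. This also stands. It would be wrong to infer that the trial cannot detect a skin benefit; any loss is confined to CEAP. Keeping the letter also adds only a limited gain, because a leg leaves C4b only when the fibrotic change has gone, within 8 weeks.

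**C4a legs can improve.** The primary objective is symptoms, and the AVVQ covers pain, oedema, itching, discoloration and eczema. VCSS pigmentation and inflammation, and the camera areas, can also change in C4a legs. A reader might infer that admitting C4a patients will inflate the next trial to between 44 and 210 patients. That range needs exactly no effect in C4a patients, and the documents do not support it.

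**It may be loose terminology.** The Eykona section treats hyperpigmentation as a change associated with lipodermatosclerosis, so the term may be meant for all class 4 changes. If so, the hypothesis, aim and objectives are the text to correct. The table, the objectives and the entry rule still cannot all stand as written.

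**Conclusion.** The population mismatch holds on the text alone: the hypothesis, aim and objectives name a C4b condition, and entry admits C4a. The results and the pilot effect and SD would describe a broader population than the one named.

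The CEAP point is conditional. If the datasheet does not keep the letter, the stated score cannot register C4b to C4a, and a flat CEAP result says nothing about that improvement.

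The size of any dilution is unknown. Over assumed C4a shares of 20% to 60% and an assumed effect of 0.5, the planning figure could stay at 34 (equal response), rise to between 42 and 67 (half response), or at worst reach 44 to 210 (no response in C4a patients). The case for a change rests on the text, not on these figures. It is worth correcting before recruitment, because it decides which patients the conclusions apply to.

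**What to change.** Keep class 4 entry and make the other texts agree with it:
- In the hypothesis, aim and both objectives, replace lipodermatosclerosis with C4 skin changes.
- In the CEAP and Statistical analysis sections, state that the clinical class is recorded per leg at each visit with C4a and C4b separate. Tabulate it by class, leg (copper or control) and visit.
- Class each leg as better, unchanged or worse than baseline in the order C3 or lower, C4a, C4b, C5, C6. Compare copper and control legs within patient, descriptively. A new ulcer then appears in the same table as C6.
- Show patients with lipodermatosclerosis in both legs separately and descriptively. Identify them by the condition itself, because C4b alone also admits atrophie blanche.

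The cost is wording and one extra table, since CEAP is already graded per leg at each visit. The downside is a small lipodermatosclerosis subgroup with imprecise estimates (see the SD limits above).

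The alternative is to require lipodermatosclerosis (C4b) in both legs at entry. This matches the present objectives but slows recruitment. At the same clinic flow, 15 patients would take 3/(1 − q) months: 3.75, 5 or 7.5 instead of 3 for assumed C4a shares of 20%, 40% or 60%. That is a trade-off for the sponsor.
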